Exclusion Criteria	
 • Body Mass Index (BMI) > 40 kg/m² • Compromised immune system based on medical history • History of valvular heart disease • Implanted cardiac pacemaker/defibrillator or Deep Brain Stimulator • Evidence of joint or overlying skin infection of the affected limb • History of recurrent skin infections • Bleeding disorder OR INR ≥ 1.5 for those on warfarin • Confounding conditions • History of nerve damage in the affected lower limb • Allergy to skin surface electrodes and/or medical-grade adhesive tapes • Allergy to all local anesthetic agents such as lidocaine or previous reaction to anesthesia • Any other medical condition that may interfere with ability to participate in a clinical trial as determined by the Investigator • Prisoners, minors, legally incompetent people, unconscious patients, house staff, or students • Pregnant • History of substance abuse within 6 months • Potential secondary gain issues
Primary Safety Endpoint	Occurrence of device-related adverse events.
Primary Clinical Endpoint	Subjects will record average pain while walking over the last 24 hours in a daily diary using the 11-point numerical rating scale (0=no pain to 10=worst pain imaginable) of the Brief Pain Inventory – Short Form (Question 5; BPI-5). The mean of the daily scores recorded will be calculated, and the primary endpoint is the mean pain score across all subjects. The primary endpoint will be compared to historical controls (e.g., published data).
Secondary Endpoints	
Pain-related outcomes
 
 • Pain intensity over the last 24 hours as recorded as Average pain on a numerical rating scale (BPI-5) using a daily diary • Pain intensity over the last 24 hours as recorded as Average pain at rest on a numerical rating scale (BPI-5) using a daily diary • Cumulative analgesic usage

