Existing treatments for postoperative pain include analgesics, continuous passive motion, cooling pads, epidural analgesia, and regional nerve blocks (anesthetic delivered continuously through a percutaneously placed catheter or as single injections). In spite of these treatments, most patients experience moderate to severe acute pain. Further, during the subacute phase, these treatments are ineffective, are not indicated for such an extended period of time or for at home use, and/or carry risks of side effects and complications. As a result, a non-opioid treatment is needed that can relieve postoperative pain following TKA with minimal side effects and can be used throughout the duration of the subacute phase. The proposed study will determine the feasibility of using PNS therapy to treat postoperative pain following TKA. The hypothesis is that percutaneous stimulation will evoke a [REDACTED] sensation [REDACTED] in the region of pain and produce clinically significant reductions in pain.

Subjects will receive leads to stimulate the nerves innervating the regions of pain or expected pain [REDACTED] up to 2 weeks prior to TKA surgery. Stimulation may be delivered up to the time of the TKA. Following TKA, stimulation will be turned on and adjusted as needed to provide pain relief. Subjects will record average pain over the last 24 hours in a daily diary using the 11-point numerical rating scale (0=no pain to 10=worst pain imaginable) of the Brief Pain Inventory – Short Form (Question 5; BPI-5). The mean of the daily scores recorded from POD0 to POD28 (i.e., first 4 weeks following TKA surgery) will be calculated, and the primary endpoint is the mean pain score across all subjects, which will be compared to historical controls (e.g., published data). Subjects will receive treatment for up to 24 hours/day for up to 60 days (i.e., leads will be indwelling for up to 60 days total). Subjects will be followed for three months following TKA surgery. The results of this study will [REDACTED] will be used to support subsequent studies of the SPR PNS therapy to treat postoperative pain following TKA.

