3.2 Primary Outcome

The primary outcome of this study will be the average daily pain while walking over the first 4 weeks following TKA surgery. This will be recorded using Question 5 of the Brief Pain Inventory Short Form (BPI-5; details of BPI below), which assesses “Average Pain” on an 11 point numerical rating scale, with one end representing “No pain” (0) and the other end representing “Pain as bad as you can imagine” (10). Subjects will record BPI-5 scores daily in a diary, and the mean score over the first 4 weeks following TKA will be calculated for each subject. The primary outcome will be compared to historical controls (e.g., published data).

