6.5.4 Day of TKA and Start of Stimulation following TKA (Visit 4)

Following TKA surgery, the bandages covering the leads will be carefully removed and the leads will be connected to the Stimulators. Stimulation will be delivered to determine if postoperative pain can be reduced. [REDACTED]

[REDACTED] Stimulation will be delivered for up to approximately 24 hours/day (except when bathing, changing the battery, etc.) until end of therapy (*i.e.*, approximately 6 weeks following TKA surgery. Leads will be indwelling for no more than 60 days total). Additionally, Visits 1, 2 and 4 may occur on the same day, such as the day of the TKA (if so, visit 3 is not required).

Stimulation parameters may be varied. [REDACTED]

[REDACTED] The care and maintenance of the stimulation system, leads, and lead exit sites will be performed by members of the clinical or study staff. Subjects will also be provided with a manual and instructed on the use and care of the device in case changes are required when clinical/study staff is not present.

Sterile, waterproof covering bandages [REDACTED] will be placed over the exit sites of the leads. Additional bandages may secure the lead connections. The site may choose to utilize a skin adhesive [REDACTED] The clinical/study staff and subject will be instructed to inspect the electrode exit site for signs of irritation and report them to the clinician. [REDACTED]

[REDACTED] The area around the leads and surface electrodes will be kept clean and dry. If bandages become wet or loose, the bandages will be changed. A bandage change will not be considered an Adverse Event (AE), but may be documented.

The following outcome measures may be assessed during Visit 3:

- Patient shaded leg diagrams of pain [REDACTED]
- Current pain treatments/analgesic usage
- Subjects will be given a diary to record their daily “Average Pain” [REDACTED] The diary will be completed for each day of treatment.

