8.1 Analysis of Outcomes and Exploratory Measures

A table of outcomes and exploratory measures to be collected during the study can be found in Appendix A.

Question 5 of the Brief Pain Inventory-Short Form (BPI-5) is an 11-point numerical rating scale rating “Average Pain”. The BPI-5 will be measured at Visit 1 to establish a baseline score, as well as daily during stimulation and monthly post-EOT. For each subject, the mean over the first 4 weeks following TKA surgery will be calculated. An overall mean across all subjects for the first 4 weeks following TKA surgery will be calculated as well. This outcome will also be compared to historical controls (e.g., published data).

Additionally, sub-analyses will be performed to determine the mean over different post-operative phases (such as acute (e.g., days 1-7) or subacute (e.g., days 7-28)); calculate the mean for each subject and across subjects up to End of Treatment (week 6); and evaluate the proportion of subjects with pain below a certain threshold (e.g., 4/10).

Subjects will also rank their daily “Average Pain” (BPI-5) while walking. These data will undergo the same analysis as listed above for the standard BPI-5. This outcome will also be compared to historical controls (e.g., published data).

At the weekly visits during stimulation, subjects will be asked to report their weekly “Average Pain” (BPI-5) while at rest. The mean over different intervals (such as weeks 1-4 or weeks 1-6) will be calculated.

At each study visit, pain treatments and analgesic usage will be recorded. Changes in analgesic usage will be calculated using morphine equivalent dosing (MED). The usage of analgesics over various intervals (such as weekly averages, during weeks 1-4, etc.) will be calculated.

Medication usage will also be compared to pain scores to examine the correlation between analgesic usage and pain. The time to cessation of opioid will be determined. Also at each study visit, subjects will be queried for opioid related side effects. The number of effects noted over various intervals will be calculated.

Range of motion [REDACTED] will be collected at visits before, during, and after treatment. The time to achieve milestones (e.g., 90 degrees flexion, 100 degrees flexion) will be calculated for each subject and across all subjects. The mean flexion, extension, and range of motion (flexion – extension) across all subjects will be determined. The same will be calculated for passive ROM and active ROM.

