8.2 Plan to maximize subject retention and minimize loss of data

Significant efforts will be made to maintain maximum subject retention and follow up data and minimize the percentage of missing data.

A potential source of data loss is the failure of the subjects to return their completed diaries. Thus, subjects may receive reminder calls from the clinical study staff before certain visits to remind them to bring their completed diaries with them to the visit.

Subject withdrawal from the study is a potential source of data loss. Study investigators and staff will be trained to have clear discussions with subjects considering withdrawing from the study.

Subjects are offered compensation for each visit as it is completed, including unscheduled visits, even if they do not complete all the visits. This compensation is intended to cover costs associated with taking the time to participate in the study. Sites are also provided with a travel budget for which they are able to reimburse subjects for the actual incurred mileage or mobility transportation arrangements can be provided.

If a subject is unable to return any follow-up diary, the data will be replaced using the one-week recall data (question #5 of the validated BPI-SF). The question may be collected verbally over the phone if needed. This method will mitigate the problem of missing data and minimize the need to impute scores. Scores will only be imputed if recall data are unavailable and cannot be obtained. If the subject later returns the diary, the diary data will be used over the one-week recall data.

Additional steps will be taken as necessary to maintain a high level of subject participation and follow up. For example, if a subject relocates during the study, arrangements will be made either to provide transportation for the subject to attend their visits at the clinical site, or to allow the subject to receive the necessary follow up at a medical center in closer proximity to their new location and a referring physician located near the subject will conduct the visit with the assistance of an investigator and/or a technical representative from SPR Therapeutics as needed.

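### The primary outcome covers a fixed four weeks after surgery, but the diary's length is worded by treatment or stimulation, so it is unclear whether daily walking scores continue to POD28 in a subject whose stimulation stops early

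*Combined protocol and SAP*

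**What the plan says.** **Outcome and window.** Section 3.2 makes the primary outcome average daily pain while walking. It asks subjects to score BPI-5 every day in a diary, with no condition attached, and "the mean score over the first 4 weeks following TKA will be calculated for each subject". Section 2.1 gives the window in days: "The mean of the daily scores recorded from POD0 to POD28 (i.e., first 4 weeks following TKA surgery) will be calculated". That sentence follows a description of average pain rather than walking pain, but it describes the primary endpoint. The Protocol Synopsis names no window: "The mean of the daily scores recorded will be calculated, and the primary endpoint is the mean pain score across all subjects".

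**How long the diary runs.**
- The Synopsis study plan ties the diary to the days of the treatment period.
- Section 6.5.4: "The diary will be completed for each day of treatment".
- Section 8.1 has BPI-5 measured at Visit 1, "as well as daily during stimulation and monthly post-EOT". Of the walking scores it says "These data will undergo the same analysis as listed above for the standard BPI-5", and it gives them no collection rule of their own.
- Section 6.5.6 has subjects reminded about their diaries at the week 1 to 5 contacts.

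**Missing diaries.** Section 8.2 says "If a subject is unable to return any follow-up diary, the data will be replaced using the one-week recall data", meaning BPI-SF question 5, and then "Scores will only be imputed if recall data are unavailable and cannot be obtained".

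**The concern.** The outcome window is counted in days from surgery, while the diary is described by treatment or stimulation. The two agree as long as stimulation runs through POD28. If stimulation ends sooner, a site could reasonably stop the daily diary that day or carry on, and the readable text supports either course. Uncollected scores cannot be recovered at analysis.

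The documents make an early stop possible but give no rate. Section 6.5.9 makes lead replacement depend partly on whether the subject wishes to go on with therapy, and section 11.2 lists lead breakage, exit-site infection and worsening pain among the risks.

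The fallback in section 8.2 covers only part of this. Its trigger is a diary the subject cannot return, not days for which a site thought no diary was due. It also does not say that the recall question is asked for pain while walking.

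**Working it through.** The plan states no figure on this point, so there is nothing to reproduce. The check is a day count followed by an illustration on assumed inputs.

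**1. Does planned treatment cover the window?** Leads go in at most 14 days before TKA and may stay at most 60 days (Synopsis; section 6.5.2). The last permitted day is 60 - 14 = POD46. End of Treatment at six weeks is POD42, which uses 14 + 42 = 56 lead-days. Both fall after POD28, so only early stoppers matter.

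**2. Days at issue.** POD0 to POD28 is 29 days. If scoring ends with stimulation on POD k, then k + 1 days are recorded and 28 - k are not.

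| Stop | Recorded | Not recorded |
|---|---|---|
| POD7 | 8 | 21 |
| POD14 | 15 | 14 |
| POD21 | 22 | 7 |

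**3. Shift in one subject's mean.** The pain curves are assumed.
- Curve A: 3 + 4·exp(-d/10), 29-day mean 4.370.
- Curve B: 4 + 2·exp(-d/10), 29-day mean 4.685.

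Let r be an assumed rise in pain on every day after the stop. Then

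shift = mean(days 0 to k) - [29-day mean + r(28 - k)/29].

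Examples for a stop at POD7:
- Curve A, r = 0: 5.893 - 4.370 = +1.52.
- Curve B, r = 2: 5.447 - (4.685 + 2 × 21/29) = 5.447 - 6.133 = -0.69.

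| Curve | r | POD7 | POD14 | POD21 |
|---|---|---|---|---|
| A | 0 | +1.52 | +0.81 | +0.33 |
| A | 1 | +0.80 | +0.32 | +0.09 |
| A | 2 | +0.08 | -0.16 | -0.15 |
| B | 0 | +0.76 | +0.40 | +0.16 |
| B | 1 | +0.04 | -0.08 | -0.08 |
| B | 2 | -0.69 | -0.56 | -0.32 |

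The sign changes at r = 2.10, 1.67 and 1.36 on curve A, and at 1.05, 0.84 and 0.68 on curve B (stops at POD7, 14 and 21).

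**4. Shift in the group mean.** This is the fraction stopping early times the subject shift. At an assumed 10% to 20% (about 4 to 7 of 36), the extremes are 0.2 × 1.52 = +0.30 and 0.2 × (-0.69) = -0.14. Each extreme needs 20% of subjects all to stop at POD7. For scale, the 95% confidence half-width for one mean at n = 36 is t(0.975, 35) × SD/6 = 2.03 × 2/6 = 0.68 at an assumed SD of 2, and 0.51 to 0.85 for SD 1.5 to 2.5.

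**5. Recall wording.** Suppose recall fills the missing days but is answered for general pain, and walking pain is 1 point higher (assumed). The subject mean is then too low by (28 - k)/29 = 0.72, 0.48 or 0.24 for a stop at POD7, 14 or 21. At group level that is 0.1 × 0.24 = 0.02 to 0.2 × 0.72 = 0.14.

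**The case against.** The strongest reply is that treatment and stimulation are phase names here. Section 8.1 contrasts the stimulation phase with the time after End of Treatment and dates End of Treatment at week 6. It also speaks of weekly visits during stimulation, and those visits are scheduled by weeks since surgery. Section 3.2 asks for daily scores without condition, and the reminders in section 6.5.6 carry none either. On this reading the diary runs to about week 6 whatever the device is doing, and there is no gap. The reading is reasonable and may well be what was meant. It stands as one of two readings, because none of these passages speaks of a subject whose stimulation has ended.

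Text is blacked out directly before the diary sentence in section 6.5.4 and in the visit lists, and the Appendix A diary row cannot be read by visit. A rule may sit there, so the point is limited to what can be read.

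The affected group is narrow. Someone who withdraws from the study gives no diary under any wording. Section 6.5.9 concerns replacing a lead and does not describe people who stop stimulation but stay in follow-up, so that route is inferred.

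On recall, the walking score and the recall item share the BPI-5 label, so sites may ask about walking anyway. Section 2.2 compares movement with rest, not walking with general average pain, so the 1-point gap has no source in the documents.

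A reader might infer more: that the protocol ends daily scoring when stimulation stops, or that it has no provision for missing diaries. The unconditional sentence in section 3.2 rules out asserting the first. Section 8.2 contradicts the second, since it provides weekly recall and then imputation.

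**Conclusion.** The concern holds as an unresolved ambiguity in how primary data are collected from early stoppers. Subjects who complete planned treatment are unaffected. If the diary follows stimulation, the later scores are lost and the mean of recorded days may be biased either way. It is too high when pain would have kept falling, and too low when pain rebounds enough after the stop.

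The illustrated group effect is -0.14 to +0.30 points, below the assumed half-width of 0.68 and also below 0.51 at SD 1.5. The early-stop rate, pain curves, rebound and SD are all assumptions. A reader might infer that the gap flatters the device or could overturn the comparison with historical controls. The documents support neither inference, because the sign is undetermined and no early-stop rate is given.

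Priority is minor. The case for acting is that the wording is easy to settle and the lost days could not be recovered.

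**What to change.** Reconcile sections 6.5.4 and 8.1 with section 3.2 by stating that the daily diary, including the score while walking, is completed from POD0 through POD28 whether or not stimulation continues, for subjects who remain in the study. In section 8.2, state that recall used in place of primary diary data is asked for pain while walking, and that it also applies to days missing after an early stop. If a redacted passage already says this, bring the readable sections into line with it. The change concerns data collection only; the mean of daily scores remains the primary estimate.

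The cost is a few extra diary days for early stoppers and a few sentences of text. The resulting mean may be less favourable.

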6.5.5 In-Hospital Treatment: (Visits 5a, b, c, etc.)

On each day of in-hospital treatment (starting at POD 1), clinical/study staff will visit the subject in the subject’s unit. If necessary, pads and/or batteries will be replaced and stimulation parameters may be adjusted. [REDACTED]

Maintenance and care of the leads and lead exit sites will be performed, including visual inspection and bandage changes, if necessary. The following outcome measures may be assessed during each Visit 5:

Pain [REDACTED]

Completion of daily diary [REDACTED]

- Range of motion ([REDACTED] and pain during ROM)
- Fixed Distance Walk Test (only at the anticipated last visit before discharge)
- TUG Test (only at the anticipated last visit before discharge)
- WOMAC (only at the anticipated last visit before discharge)

BPI-9 [REDACTED]

- Patient Global Impression of Change (PGIC) (only at the anticipated last visit before discharge)
- Time to recovery milestones
- Current pain treatments/analgesic usage
- Assess for opioid-related side effects

In addition, subjects will be queried for adverse events. Outcomes requiring physical function of the subject (such as Fixed Distance Walk Test or TUG Test) must be assessed by the physical therapy staff for the in-hospital visits. All functional outcomes will only be administered if deemed safe by the staff. If it is deemed unsafe to complete a test or if the subject is unable to complete a test, it will not be considered a protocol deviation.

6.5.6 Post-Discharge Treatment: Weeks 1 through 5 after TKA surgery (Visits 6-10)

Visits will occur 1 week (Visit 6), 2 weeks (Visit 7), 3 weeks (Visit 8), 4 weeks (Visit 9), and 5 weeks (Visit 10) after TKA surgery. The 2-week visit will occur in person; all other visits may be completed via telephone. Subjects will be reminded to complete their daily pain diaries. In addition, subjects will be queried for adverse events.

Subjects will continue to be followed regardless of discharge location (home, inpatient rehabilitation facility, outpatient rehabilitation facility). Sites should make every effort to work with outside facilities to ensure the subject can return to the clinic.

The following outcome measures may be assessed during the Visit 6, 8, 9 and 10 telephone calls:

BPI-5 [REDACTED]

Pain [REDACTED]

BPI-9 [REDACTED]

- PGIC
- Time to recovery milestones
- Current pain treatments/analgesic usage
- Assess for opioid-related side effects

In addition to the above, the following may be assessed during the Visit 7 in-person evaluation or any other post-discharge treatment visits conducted in person:

- Inspection of bandages and lead exit site
- Adjustment of stimulation parameters (as needed)
- ROM [REDACTED] and pain during ROM
- Six-Minute Walk Test
- TUG Test

- WOMAC

6.5.7 End of Treatment: 6 weeks after TKA surgery (Visit 11)

The End of Treatment will occur 6 weeks after TKA surgery. The lead must be removed within 60 days of lead placement. Prior to lead removal, additional electrical stimulation testing may be conducted in the clinic. In addition, subjects will be queried for adverse events.

The following outcome measures may be assessed:

- BPI-5 [REDACTED]
- Pain [REDACTED]
- ROM [REDACTED] and pain during ROM
- Six-Minute Walk Test
- TUG Test
- WOMAC
- BPI-9 [REDACTED]
- PGIC
- Subject Satisfaction Survey
- PCS
- Time to recovery milestones
- Current pain treatments/analgesic usage
- Assess for opioid-related side effects

At the conclusion of this visit, the leads will be removed [REDACTED] and will be examined to confirm that they are intact upon removal. The Investigator will perform a visual inspection of the removed leads. If results of the visual inspection are suggestive of a broken lead or retained fragment, a radiograph may be taken to confirm the presence or absence of retained fragment(s). The Investigator will determine what is medically required to further evaluate and treat the subject for the retained fragment.

6.5.8 Follow-up Visits: Visits 12-(2 months), Visit 13 (3months)

Visits will occur at 2 months (Visit 12) and 3 months (Visit 13) after TKA surgery. The 2-month visit may be completed via telephone and the 3-month visit will occur in person. At each visit, subjects will be queried for AEs.

The following outcome measures may be assessed during the Visit 12 telephone call:

- BPI-5 ([REDACTED])
- BPI-9 [REDACTED]
- PGIC
- Time to recovery milestones
- Current pain treatments/analgesic usage
- Assess for opioid-related side effects

In addition to the above, the following may be assessed during the Visit 13 in-person evaluation:

[figure not shown]
- Inspection of lead exit site
- Diagram of pain [REDACTED]
- ROM [REDACTED] and pain during ROM
- Six-Minute Walk Test
- TUG Test

- WOMAC
- PCS

In addition, subjects will be queried for adverse events. If no AEs are noted, the subject will be discharged from the study following the 3-month visit. Any AE will be documented, addressed, and followed to resolution.

